5.3 Guidance on the management adverse events

Excluded reporting and recording of adverse events:

1. Alopecia
2. Differential component of CBC except WBC, ANC, platelet count and hemoglobin

Baseline reporting of adverse events prior to protocol treatment will not be recorded or reported. All other baseline adverse events will be reviewed and if worsen will be captured in Figures 2-9.

The eligibility criteria provide an extensive list of concomitant medication as exclusions. Non-Oncologic concomitant medications will not be reported.

5.3.1 Guidance on dose reduction for specified alterations in amylase, lipase, or liver enzymes.

Figure 1. CNS Adverse Event Management
Study drug dosing is for 10 total weeks. During treatment visits will correspond to the week the patient is actively administering drug.

[figure not shown]

Figure 3. Elevated Amylase and Lipase at any dose

Study drug dosing is for 10 total weeks. During treatment visits will correspond to the week the patient is actively administering drug.

[figure not shown]
[figure not shown]

Figure 4. Management of elevated AST or ALT

Study drug dosing is for 10 total weeks. During treatment visits will correspond to the week the patient is actively administer

5.3.1.1 Guidance for all other Adverse Events

Figure 5. Non AST, Non ALT, Non Amylase, Non Lipase And Non CNS Adverse Event (All other adverse events) Management
Study drug dosing is for 10 total weeks. During treatment visits will correspond to the week the patient is actively administering drug.

[figure not shown]

Figure 6. Grade 3 Non CNS Adverse Event Management Not assessed under Figure 4
Study drug dosing is for 10 total weeks. During treatment visits will correspond to the week the patient is actively administering drug.

[figure not shown]

Figure 7. Any Grade 2 deemed NOT possibly related to other systemic treatment

[figure not shown]

Figure 8. CNS Adverse Event Management NOT related to study drug (possible, probable or definite attribution)
Study drug dosing is for 10 total weeks. During treatment visits will correspond to the week the patient is actively administering drug.

[figure not shown]
[figure not shown]

Figure 9. Grade 3 Non CNS Adverse Event Management Possibly related to study drug and Possibly related to other oncologic systemic treatment
Study drug dosing is for 10 total weeks. During treatment visits will correspond to the week the patient is actively administering drug.

5.3.2 On-treatment pregnancy

Positive blood or urine Hcg will result in immediate discontinuation of the drug and referral to gynecology.

6.0 Statistical Considerations

6.0 Statistical Considerations

Sample Size

The primary outcome for this study is time to pleural catheter removal because it is no longer needed to drain the pleura of fluid. Patients who have their catheter removed for other reasons will be censored as of the date of catheter removal. Patients who die before having their catheter removed will be censored on the date of death.

Preliminary data from 58 breast cancer patients with ECOG performance status 0, 1, 2, or 3 revealed a median time to catheter removal of 110 days with 95% confidence interval 56 to 328 days. Twenty-nine of these 58 patients had their catheters removed because they were no longer needed to drain the pleura of fluid.

Patients will be randomized to active treatment (valproic acid) or control. A sample size of 76 patients (38 on each arm) will yield 80% power to detect an improvement in median time to catheter removal from 56 days in the control arm to 28 days (hazard ratio = 2.0) in the active treatment arm with a 2-sided significance level of 0.05. We expect to enroll 3 patients per month. We will be able to detect a hazard ratio of 2.0 (control vs. experimental), regardless of the median for the control group. If the median for the control group is actually 110 days, then we will be able to detect a significant difference if the median in the experimental group is 55 days.

This sample size calculation includes an interim analysis for futility and for efficacy once 36 patients have had their catheters removed using the methods of Lan and DeMets. The interim analysis for efficacy will employ an O'Brien-Fleming stopping boundary with a nominal significance level of 0.0031, while the interim analysis for futility will employ a Pockock stopping boundary with a nominal significance level of 0.3217. The final analysis will use a nominal significance level of 0.049 and will be conducted after all patients have had their catheters removed. These sample size calculations were performed with East 5.0 (Copyright © 2007, Cytel Inc., Cambridge, MA). Sample size was calculated based on 50% reduction in median time to catheter removal secondary to improved fluid in the control.

Randomization

Patients will be randomized to active treatment or control stratified by lung re-expansion ($\geq 80\%$ lung re-expansion, $<80\%$ lung re-expansion), ECOG performance status (0-1, 2, 3), using the Clinical Trial Conduct website (<https://biostatsitics.mdanderson.org/ClinicalTrialConduct>), which is housed on a secure server at MDACC and maintained by the MDACC Department of Biostatistics. Access to the website will be gained through usernames and passwords provided by the MDACC Department of Biostatistics to personnel responsible for enrolling patients and reviewing and analyzing patient data. Training on the use of the Clinical Trial Conduct website to randomize and enroll patients on the study will be provided by the study statistician. Investigation Pharmacy will have access the Clinical Trial Conduct website

to review the patient assignment. The IND office will be notified if an event occurs leading to the un-blinding of the randomization.

Toxicity Monitoring

We will use the methods described by Thall et al. (1995) to monitor the rate of toxicity leading to dose reduction for patients on active treatment. Because the study is blinded to the investigators, the study statistician will monitor the toxicity monitoring rule for the active treatment arm. Toxicity data leading to dose reduction will be forwarded to the study statistician as they accrue in the form of an email with the patient study identifier and a description of the toxicity leading to dose reduction.

If the rate of toxicity leading to dose reduction for patients on active treatment is more than 25% the study will be stopped. We will enroll a minimum of 10 and a maximum of 40 patients on active treatment. We will stop the study early if $P(\text{toxicity leading to dose reduction for patient on active treatment} > 25\% | \text{data from the study}) > 0.975$. That is, given the toxicity outcomes from the patients on active treatment, if we determine that there is more than a 97.5% chance that the rate of toxicity leading to dose reduction is more than 25% we will stop the study. This decision rule gives the following stopping rule. We assume a uniform prior distribution for the rate of toxicity leading to dose-reduction. Stop the study if

[# of pts on active treatment with toxicity leading to dose reduction / # of pts evaluated]
> 6/10, 8/15, 9/20, 11/25, 13/30, 14/35, 16/40

The operating characteristics of this study design are shown in the table below.

Operating Characteristics of Toxicity Monitoring Rule					
Rate of Toxicity Leading to Dose Reduction	Probability of Stopping Early	Sample Size			
		P_{25}	P_{50}	P_{75}	
0.20	0.020	40	40	40	
0.25	0.071	40	40	40	
0.30	0.205	40	40	40	
0.35	0.407	20	40	40	
0.40	0.636	15	30	40	
0.45	0.827	10	20	35	

Analysis

We will use summary statistics to describe the demographic and clinical characteristics of patients on each treatment arm.

Primary Outcome

Time to catheter removal will be measured from the date of placement of the catheter to the date it is removed. Removal of the catheter because it is no longer needed to drain the pleura will be considered an event. Removal of the catheter for other reasons will be considered competing risks. Patients who die before their catheter is removed will be considered censored on the date of death. We will use the methods described by Gooley et al. (1999) to estimate the cumulative distribution of time to catheter removal stratified by treatment arm and randomization strata.

We will use Cox (1972) proportional hazards regression to model time to catheter removal as a function of treatment arm, cytology, and lung re-expansion, as well as other potential prognostic factors, including ECOG performance status, the number of circulating tumor cells in the peripheral blood and in the pleural effusion.

Secondary Outcomes

We will use summary statistics to describe the amount of pleural fluid drainage by treatment arm, and we will use a two-sample t-test to compare treatment arms with respect to the mean amount of pleural fluid drainage. If the usual normality assumptions do not hold we will use the Mann-Whitney test to compare treatment arms with respect to the median amount of pleural fluid drainage.

We will compare treatment arms with respect to tumor burden using a Cochran-Mantel-Haenszel chi-square test stratified by concomitant therapy. Tumor burden will be assessed with chest cat scan during week 10.

We will use summary statistics to describe symptom burden dyspnea and exercise tolerance changes and dyspnea as measured by the EQ-5D and St George's respiratory questionnaire at baseline and again at weeks 2, 6, and 10. We will use repeated measures analysis of variance methods to assess differences between treatment arms with respect to QOL, dyspnea and exercise tolerance

Toxicity

We will estimate the rate of toxicity leading to dose reduction for patients on the active treatment with a 90% credible interval. If we have toxicity leading to dose reduction in 5 of the 40 patients on the active treatment, then our 90% credible interval for the rate of toxicity leading to dose reduction will be 6.6% to 23.6%. We will also report the posterior probability that the rate of toxicity leading to dose reduction for patients on the

active treatment is more than 25%.

We will tabulate adverse events by treatment arm, grade, and relationship to study drug.

Translational Studies

For CTC studies using the adnagen approach .3 ng/ml in GA733-2 or muc-1 will be considered positive and both conversion to negative and change from baseline (using continuous data) will be assessed. Descriptive statistics will be applied. Using the Veridex system 5 CTCs will be considered positive for all dichotomous analyses and conversion to negative and change from baseline will be assessed as above.

Statistically significant conversion to negative in the VPA arm in either test will be considered a significant change. CTC studies will be performed only if funds are available and will be done by [name] who has extensive experience with both tests.

For quiescence and stem cell analysis flow cytometry will be performed for cell cycle, CD44+CD24-CD45-Epcam+ and aldefluor. Samples will be divided into three replicates to address run variability. Total percent quiescent (G1/G0) epithelial cells will be the primary metric for correlative evaluation although quiescence within stem cell populations will be assessed and reported. All data are continuous variables.

Dichotomous analysis will be based on values > or <= to the median for the entire dataset for each variable. All biomarker analyses related to outcome will be performed according to REMARK guidelines incorporating time to metastases, extent of metastatic disease (multiple vs. effusion only), triple negative vs. not, extent of prior therapy, and KPS. Analysis will include correlation between percent quiescent cells and time to catheter removal in both arms and change in percent quiescent cells from baseline in both arms. Given there will be significant variation in the baseline G0/G1 measurement we will consider a 30% relative increase in G0/G1 from baseline significant.

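### Section 6.0 states 80% power for 76 patients, but its own design needs about 76 successful-removal events; with the futility rule, power for a hazard ratio of 2.0 is nearer 60–75%

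*Combined protocol and SAP*

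**What the plan says.** The power statement in Section 6.0 (Sample Size) is given in patients: "A sample size of 76 patients (38 on each arm) will yield 80% power to detect an improvement in median time to catheter removal". The medians assumed are 28 days on active treatment against 56 on control, tested at a two-sided level of 0.05. The same section limits the event to removal because drainage is no longer needed. Of the others it says "Patients who have their catheter removed for other reasons will be censored as of the date of catheter removal" and "Patients who die before having their catheter removed will be censored on the date of death". The Primary Outcome paragraph also counts only needed-no-longer removals as events.

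The pilot series had a median of 110 days (95% CI 56 to 328), and "Twenty-nine of these 58 patients had their catheters removed because they were no longer needed to drain the pleura of fluid". No required number of events, event probability or allowance for censoring is given. The plan adds: "We will be able to detect a hazard ratio of 2.0 (control vs. experimental), regardless of the median for the control group".

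One interim analysis takes place "once 36 patients have had their catheters removed", with an O'Brien-Fleming efficacy level of 0.0031 and, for futility, a "Pockock stopping boundary with a nominal significance level of 0.3217". The final analysis uses 0.049 and "will be conducted after all patients have had their catheters removed".

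**The concern.** A number of patients equals a number of events only when nobody is censored. Here the population is one in which many patients die or lose the catheter for other reasons, and Section 1.1 quotes a median survival of 7.4 months for breast cancer effusion. If 76 is the number of events the design needs, then 76 patients are too few for the stated power. A null result would be read against a 20% risk of missing a true hazard ratio of 2.0 when the real risk is larger.

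The claim that power does not depend on the control median has the same weakness. It is true for a fixed number of events, and the plan fixes none. The nominal levels also hold only at the information fraction for which they were computed, and the plan does not secure that fraction.

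**Working it through.** **Reproducing the plan's figure.** Inputs from Section 6.0: two-sided 0.05, power 80%, hazard ratio 2.0, 1:1 allocation, Lan-DeMets O'Brien-Fleming-type efficacy, Pocock-type futility. Half information (t = 0.5) is inferred from the printed levels.

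- Fixed design (Schoenfeld): 4(1.960 + 0.842)² / (ln 2)² = 65.3 events.
- Efficacy spending at t = 0.5: 4[1 − Φ(2.241/√0.5)] = 0.00305, so z = 2.963. The final critical value is 1.9686, nominal 0.0490.
- Futility spending: 0.20 × ln(1 + (e − 1) × 0.5) = 0.124.
- With D events, the expected final z is ln 2 × √(D/4), and √t times that at the interim. Power = P(Z₁ ≥ c₁) + P(b < |Z₁| < c₁, Z₂ ≥ c₂).
- Solving for 80% power gives D = 76.4 events and b = 0.991, nominal 0.3217. Without futility, D = 65.6.

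All three printed levels are recovered, and the event count equals the stated patient count. At exactly 76 events with the look at 38, power is 79.8%.

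**Power by overall share of the 76 patients with a successful removal** (hazard ratio 2.0, printed futility level applied at 36 events, efficacy boundaries recomputed at 36/D):

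| Share | Events | Power |
|---|---|---|
| 60% | 46 | 64% |
| 70% | 53 | 69% |
| 80% | 61 | 73% |
| 90% | 68 | 77% |
| 100% | 76 | 79% |

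**Scenarios from the plan's figures.** Assumptions: exponential cause-specific hazards, with the same competing hazard c in both arms. For removal hazard l and time limit τ, an arm's event share is l/(l + c) × [1 − exp(−(l + c)τ)]. Without a limit this reduces to a ratio of medians. 7.4 months is taken as 225 days. Expected events = 38 × (control share + active share).

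1. Control median 110 days, all 29 pilot non-events taken as competing events (competing median 110): 38 × (0.500 + 0.667) = 44.3.
2. 110 days, deaths only: 225/(225 + 110) = 0.672 and 225/(225 + 55) = 0.804; 38 × 1.476 = 56.1.
3. 56 days, competing hazard of (1): 110/(110 + 56) = 0.663 and 110/(110 + 28) = 0.797; 38 × 1.460 = 55.5.
4. 56 days, deaths only: 225/(225 + 56) = 0.801 and 225/(225 + 28) = 0.889; 38 × 1.690 = 64.2.

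Each cell below is without a limit / with the 180-day limit of Section 7.1. The futility column has the look at 36 events; the no-futility column has the efficacy look at half the events. The simulation is log-rank, 4,000 replicates, 3 patients per month, futility look at the 36th event.

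| Scenario | Events | Power, futility applied | Simulated | Power, no futility |
|---|---|---|---|---|
| 1 | 44.3 / 41.5 | 62% / 60% | 60.5% / 60.1% | 63% / 61% |
| 2 | 56.1 / 49.5 | 71% / 67% | 68.5% / 66.4% | 74% / 68% |
| 3 | 55.5 / 54.5 | 71% / 70% | 68.3% / 69.3% | 73% / 72% |
| 4 | 64.2 / 62.1 | 75% / 74% | 73.2% / 72.5% | 79% / 78% |
| No competing events, 56 days | 76.0 / 71.5 | 79% / 77% | 75.2–76.2% / 76.2% | 86% / 83% |

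With no competing events but a 110-day median and the 180-day limit, 59.8 events give 73%. Across scenarios 1–4 with futility at 36 events, the hazard ratio detectable with 80% power is about 2.1 to 2.4.

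**Interim levels.** The printed levels belong to t = 0.5, which is 38 of 76. At 36 of 76 the same design gives 0.0023, 0.364 and 0.0493. If 36 means successful removals, the look falls at 36/64.2 = 56% to 36/41.5 = 87% of the information in scenarios 1–4. The Lan-DeMets efficacy and final levels would be about 0.0055 and 0.0482 at 56%, and 0.0255 and 0.0426 at 81%, against the printed 0.0031 and 0.049.

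**Final analysis.** Section 6.0 waits for all catheters to be removed, which does not provide for patients who die with one in place. Section 3.4 (evaluations beyond week 10) follows patients to removal or death, while Section 7.1 ends study participation at 180 days with the catheter in place.

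**The case against.** The nominal levels follow from alpha, beta, the spending functions and the information fraction, so matching them shows t = 0.5 whatever the sample size. That 76 is an event count is an inference from the further match on 76 itself. Another reading also fits: 36 is half of 72, and 76 patients with a 56-day control median, a 180-day limit and no competing events give 71.5 events. This cannot be excluded, but power at 72 events with futility is about 78%, and it still assumes no deaths and no other removals.

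The low end of the range rests on facts that the plan does not give. Scenarios 1 and 3 treat every pilot non-event as a competing event, though some catheters may still have been in place. Scenario 3 also joins a hazard calibrated at 110 days to a 56-day median. Without these two, the range is 67–75%. Replacement of dropouts (Section 7.2) would restore some events and is not counted, because its extent is unstated. Part of the gap to 80% is also not censoring: with no competing events the simulation gives about 76%, against 79% by formula.

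The futility rule can be treated as non-binding. If it is never applied, about 66 events suffice and scenario 4 reaches 79%. However, Section 6.0 says that its calculation includes futility, and all four scenarios stay below 80% on either basis.

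Lastly, Lan-DeMets methods exist to recompute efficacy boundaries at the observed information, so the printed levels can be read as planning values. That is reasonable, but the plan does not say so, and the final analysis is fixed at 0.049.

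**Conclusion.** The concern holds. As written, 76 patients do not give 80% power for a hazard ratio of 2.0 unless nearly all of them have a successful removal: essentially all with the futility rule, about 86% (65.6/76) without it. In the four scenarios the risk of missing a true hazard ratio of 2.0 is about 25–40% with futility applied, against the stated 20%. The direction is secure. The size depends on why 29 of the 58 pilot patients had no event, which the plan does not say, and on exponential hazards, an equal competing hazard in both arms, and applying the 7.4-month survival from catheter placement. The statement that power is independent of the control median is correct only for a fixed number of events. The interim count and the printed levels do not agree if 76 is the final event count, and the trigger for the final analysis is incomplete. This must be fixed, because it concerns the stated power and stopping levels of the primary endpoint.

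**What to change.** Keep 76 patients and restate Section 6.0 in events, on one basis (futility rule applied). Suggested text:

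> We assume that __% of control and __% of active patients will have a successful removal (source: __). 76 patients are then expected to give __ successful removals and __% power for a hazard ratio of 2.0 with the futility rule applied, or 80% power for a hazard ratio of __.

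The statistician fills the blanks after stating why 29 of the 58 pilot patients had no event. As an illustration only, an overall share of 70% would give 53 events and about 69% power with the look at 36.

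Also:

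- Limit the claim about the control median to a fixed number of events.
- Define the interim as a stated number of successful removals, and recompute both efficacy and futility boundaries at the actual information fraction. The printed levels should not be carried over; re-solving at half of 44 events, for example, gives a futility level of about 0.30.
- Trigger the final analysis when every patient has had a successful removal, another removal, death, or reached the end of follow-up. Sections 3.4 and 7.1 must first be reconciled on when follow-up ends.

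The cost is rewording, a re-run of the design software and a less favourable power statement; no patients or visits are added. Collecting 76 events instead would need about 90–140 patients in the four scenarios. At 3 per month that is 30–47 months of accrual rather than about 25 (76/3), and it is not proposed here.

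### The interim trigger (36 catheter removals, reason not stated) does not match the printed stopping levels, which fit a look at about 38 of 76 primary events

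*Combined protocol and SAP*

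**What the plan says.** All of this is in the combined protocol and SAP, Section 6.0, unless noted.

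- **Primary event:** "The primary outcome for this study is time to pleural catheter removal because it is no longer needed to drain the pleura of fluid".
- **Other removals (Sample Size):** "Patients who have their catheter removed for other reasons will be censored as of the date of catheter removal". The Primary Outcome paragraph of the same section says: "Removal of the catheter for other reasons will be considered competing risks". On either wording they are not events. Section 7.1 lists what they may be, including blockage, infection, intractable pain and a dislodged cuff.
- **Deaths with the catheter in place:** "Patients who die before having their catheter removed will be censored on the date of death".
- **Size:** "A sample size of 76 patients (38 on each arm) will yield 80% power", at a hazard ratio of 2.0 and two-sided 0.05.
- **Interim:** it takes place "once 36 patients have had their catheters removed", by the Lan-DeMets method. Efficacy uses an O'Brien-Fleming boundary at 0.0031. Futility uses a "Pockock stopping boundary with a nominal significance level of 0.3217". The final level is 0.049.

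No target number of primary events is given for either look. Nothing says that the limits will be recalculated if the look falls at a different amount of information.

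**The concern.** Two things do not line up. First, the trigger counts catheters removed without giving a reason, while the log-rank information at the look depends only on removals because drainage is no longer needed. Read literally, 36 is therefore an upper limit on the number of primary events at the interim. Second, even if all 36 are primary events, 36 of 76 is not the look for which the printed levels were derived.

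The consequence falls on futility. A fixed p-value cut-off is harder for an effective drug to clear when there are fewer events, so an early look spends more type II error than the Pocock-type plan intended. What is at stake is wrongly abandoning valproic acid when the assumed effect is real.

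**Working it through.** **Inputs (Section 6.0):** hazard ratio 2.0, 1:1 allocation, two-sided 0.05, power 80%, one interim look, levels 0.0031, 0.3217 and 0.049. The spending functions are the Lan-DeMets forms of the two named boundaries.

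**Formulas.** With d events, the log-rank z has mean ln(2)·√d/2. With t the information fraction:
- Alpha spent (one-sided 0.025): 2[1 − Φ(2.2414/√t)].
- Beta spent: 0.20·ln[1 + (e − 1)t].
- Futility limit: z = ln(2)·√d/2 + Φ⁻¹(beta spent).

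**Step 1: reproduce the plan.** With t = 0.5 and non-binding futility, the maximum is 76.2 events, against 76 stated. At d = 38, the alpha spent is 0.001525 one-sided, or 0.00305 two-sided. The final level is 0.0490. The beta spent is 0.20·ln(1.859) = 0.1240, so the futility limit is 2.137 − 1.155 = 0.981, two-sided p = 0.326.

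| Look | Efficacy | Final | Futility |
|---|---|---|---|
| Printed | 0.0031 | 0.049 | 0.3217 |
| 38 of 76 | 0.00305 | 0.0490 | 0.326 |
| 36 of 72 | 0.00305 | 0.0490 | 0.355 |
| 36 of 76 | 0.00225 | 0.0493 | 0.368 |

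The futility level is not matched to four decimals: it is 0.3264 for a 76-event design and 0.3196 for 77, with the printed value between them. Binding futility does not fit (71.9 events, final level 0.060). Reading 0.3217 as one-sided gives a 4.7% stop at 38 events, far from the 12.4% spend. The efficacy and final levels alone fit any 50% look; the futility level and the sample size are what point to 38 of 76.

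**Step 2: the printed futility cut-off at fewer events.** A two-sided 0.3217 is z = 0.991. The stop probability at a hazard ratio of 2.0 is Φ(0.991 − ln(2)·√d/2).

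| Primary events at look | Mean z | Futility stop |
|---|---|---|
| 38 | 2.137 | 12.6% |
| 36 | 2.079 | 13.8% |
| 30 | 1.898 | 18.2% |
| 24 | 1.698 | 24.0% |
| 18 | 1.470 | 31.6% |

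The planned spend is 12.4% at 38 of 76 and 11.9% at 36 of 76. The rows for 30, 24 and 18 assume that 6, 12 and 18 of the 36 removals (17%, 33%, 50%) are for other reasons. Those shares are assumptions.

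**Step 3: power if all 36 are primary events and 76 events are reached.** Power is P(Z₁ ≥ 2.958) + P(0.991 ≤ Z₁ < 2.958, Z₂ ≥ 1.969), where Z₂ has mean ln(2)·√76/2 = 3.021 and correlation √(d/76) with Z₁. It is 79.8% for a look at 38 and 78.8% for a look at 36.

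**Step 4: type I error.** With the printed levels applied at 18 to 38 events, the two-sided error is at most 0.0511.

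**The case against.** The sponsor can fairly say that Section 6.0 uses catheter removal as shorthand for the primary event: it defines the outcome once and then drops the reason, for example when giving the medians. On that reading the 36 are successful removals and the loss is one percentage point of power. This stands as a plausible reading. It does not settle the text, because the same section adds the reason when describing the preliminary data: "Twenty-nine of these 58 patients had their catheters removed because they were no longer needed to drain the pleura of fluid". Nor does it bring 36 into line with the printed levels.

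The sponsor can also say that the Lan-DeMets method exists to recompute limits at the observed information, so the levels are planned values. That may be the intent, but the text prints fixed numbers and never says they will be recalculated.

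A reader might infer a stronger claim: that half of the removals will be for other reasons, so that an effective drug is stopped about a third of the time and power falls far below 80%. The documents do not support this. The 29 of 58 is a share of patients, and its denominator may include deaths and catheters still in place; it is not a share of removals. An overall power computed for those cases on 76 final events would also contradict itself, because 76 patients cannot supply 76 primary events if some removals are not events.

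**Conclusion.** The trigger and the printed levels disagree and should be reconciled. The size depends on what the 36 are. If all are primary events, the effect is small: a futility stop of 13.8% against 12.6%, and power of 78.8% against 79.8%, assuming 76 final events. If the trigger is applied literally and some removals are for other reasons, the chance of wrongly stopping for futility at a hazard ratio of 2.0 rises to between 18% and 32% for 30 down to 18 primary events. Those figures rest on an assumed share and show the direction and range; they are not a forecast. The type I error is not a concern. A general statement that the plan fails to deliver 80% power because of this trigger goes further than the documents allow.

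**What to change.** In Section 6.0:

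1. Define the interim trigger as a number of primary events, meaning removals because drainage is no longer needed.
2. State the target number of primary events for the final analysis.
3. Place the look at half of that target: 38 if the target is 76.
4. State that both limits are recomputed from the named spending functions at the observed information fraction, with 0.0031 and 0.3217 as planned values only. At 36 of 76, for example, they become 0.0023 and about 0.368.

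The trigger and the final target have to be set together. If the preliminary share of patients applied, 76 × 29/58 = 38 successful removals would be all that the trial yields, and a look fixed at 38 would fall at its end.

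The cost is protocol and SAP wording, an interim that may come later (materially later if many removals are for other reasons), and a restated power if fewer than 76 primary events are expected.
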